8.1.1 Poststudy Treatment Study Follow-up

In this study, ORR is the primary endpoint of the study. Poststudy follow-up is of critical importance and is essential to preserving participant safety and the integrity of the study. Participants who discontinue study drug must continue to be followed for collection of outcome and/or survival follow-up data as required and in line with [Section 5](#) until death or the conclusion of the study.

BMS may request that survival data be collected on all treated/randomized participants outside of the protocol-defined window (see [Section 5](#)). At the time of this request, each participant will be contacted to determine their survival status unless the participant has withdrawn consent for all contacts or is lost to follow-up.

8.2 Discontinuation from the Study

Participants who request to discontinue study treatment will remain in the study and must continue to be followed for protocol-specified follow-up procedures. The only exception to this is when a participant specifically withdraws consent for any further contact with him/her or persons previously authorized by participant to provide this information.

- Participants should notify the investigator of the decision to withdraw consent from future follow-up **in writing**, whenever possible.
- The withdrawal of consent should be explained in detail in the medical records by the investigator, as to whether the withdrawal is from further treatment with study treatment only or also from study procedures and/or post treatment study follow-up, and entered on the appropriate CRF page.

- In the event that vital status (whether the participant is alive or dead) is being measured, publicly available information should be used to determine vital status only as appropriately directed in accordance with local law.
- If the participant withdraws consent for disclosure of future information, the sponsor may retain and continue to use any data collected before such a withdrawal of consent.

8.3 Lost to Follow-up

- All reasonable efforts must be made to locate participants to determine and report their ongoing status. This includes follow-up with persons authorized by the participant.
- Lost to follow-up is defined by the inability to reach the participant after a minimum of 3 documented phone calls, faxes, or emails as well as lack of response by participant to 1 registered mail letter. All attempts should be documented in the participant's medical records.
- If it is determined that the participant has died, the site will use permissible local methods to obtain date and cause of death.
- If investigator's use of third-party representative to assist in the follow-up portion of the study has been included in the participant's informed consent, then the investigator may use a Sponsor-retained third-party representative to assist site staff with obtaining the participant's contact information or other public vital status data necessary to complete the follow-up portion of the study.
- The site staff and representative will consult publicly available sources, such as public health registries and databases, in order to obtain updated contact information.
- If after all attempts, the participant remains lost to follow-up, then the last known alive date as determined by the investigator should be reported and documented in the participant's medical records.

9 STUDY ASSESSMENTS AND PROCEDURES

- Study procedures and timing are summarized in the Schedule of Activities.
- Protocol waivers or exemptions are not allowed.
- All immediate safety concerns must be discussed with the Sponsor immediately upon occurrence or awareness to determine if the participant should continue or discontinue treatment.
- Adherence to the study design requirements, including those specified in the Schedule of Activities, is essential and required for study conduct.
- All screening evaluations must be completed and reviewed to confirm that potential participants meet all eligibility criteria before randomization. The investigator will maintain a screening log to record details of all participants screened and to confirm eligibility or record reasons for screening failure, as applicable.
- Procedures conducted as part of the participant's routine clinical management (eg, blood count) and obtained before signing of informed consent may be utilized for screening or baseline purposes provided the procedure meets the protocol-defined criteria and has been performed within the timeframe defined in the Schedule of Activities.

Additional measures, including nonstudy required laboratory tests, should be performed as clinically indicated or to comply with local regulations. Laboratory toxicities (eg, suspected drug induced liver enzyme evaluations) will be monitored during the follow-up phase via on site/local labs until all study treatment-related toxicities resolve, return to baseline, or are deemed irreversible.

If a participant shows pulmonary-related signs (hypoxia, fever) or symptoms (eg, dyspnea, cough, and fever) consistent with possible pulmonary adverse events, the participant should be immediately evaluated to rule out pulmonary toxicity, according to the suspected pulmonary toxicity management algorithm in [Appendix 8](#).

For those participants receiving on-going treatment with BMS-986213 or nivolumab, troponin elevations will require the participant to undergo a cardiac evaluation. Following this evaluation, determination of further treatment will be based on the discussion with the BMS Medical Monitor or designee.

Some of the assessments referred to in this section may not be captured as data in the eCRF. They are intended to be used as safety monitoring by the treating physician. Additional testing or assessments may be performed as clinically necessary or where required by institutional or local regulations.

9.1 Efficacy Assessments

9.1.1 Imaging Assessment for the Study

Images will be submitted to an imaging core lab for BICR. Sites should be qualified prior to scanning the first participant and understand the image acquisition guidelines and submission process as outlined in the CA224060 Imaging Manual to be provided by the imaging core lab.

Screening images should be acquired as outlined in [Table 2-1](#). On study images should be acquired as outlined in [Table 2-2](#), [Table 2-3](#), and [Table 2-4](#) from the date of randomization until participant has confirmed progression by BICR, subsequent therapy is started, withdraw of consent, or participant is lost to follow up.

Every attempt should be made to image each participant using an identical acquisition protocol on the same scanner for all imaging time points.

Tumor assessments at other time points may be performed if clinically indicated and should be submitted to the central imaging vendor.

Any additional imaging that may demonstrate tumor response or progression (including scans performed at unscheduled time points and/or at an outside institution) should be collected for RECIST 1.1 tumor assessment and submitted to the BICR.

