Table 2-2: On-treatment Assessments - Participants Assigned to Investigator’s Choice XELOX or SOX (CA224060)

Procedure ^a	Cycle 1 Day 1 (Cycle = 6 weeks)	Other Time Points Relative to Dosing Schedule	Notes
			
progression (PD) or the participant withdraws consent, whichever comes first. Participants who discontinue study treatment for reasons other than PD will continue to have tumor assessments until their disease progresses or they withdraw consent.
 
Use same imaging method as was used at screening/baseline.

Brain Imaging		See note	
See Section 9.1.1. Participants with a history of brain metastases or symptoms should have surveillance MRI per standard of care (approximately every 12 weeks), or sooner if clinically indicated.

Study Treatment			
Randomization	X		Contact IRT for randomization.

Table 2-2: On-treatment Assessments - Participants Assigned to Investigator’s Choice XELOX or SOX (CA224060)

Procedure ^a	Cycle 1 Day 1 (Cycle = 6 weeks)	Other Time Points Relative to Dosing Schedule	Notes
BMS-986213 or Nivolumab	X	See note	
First dose of BMS-986213 or nivolumab and chemotherapy (XELOX or SOX) should be administered within 72 hours after randomization. BMS-986213 or nivolumab should be administered on the same day as the chemotherapy, unless there is a dose delay or treatment is discontinued. BMS-986213 or nivolumab must be administered within 3 days before or after the scheduled date.
 
BMS-986213 should be administered in a single IV bag over 60 minutes. Nivolumab should be administered over 30 minutes.

XELOX or SOX and Dispense Drug Diary	X	See note	
First dose to be administered within 72 hours after randomization.
 
 • XELOX dose schedule: see Table 7.1.2-1. Subsequent XELOX doses may be administered within dosing windows per package insert or local standard. • SOX dose schedule: see Table 7.1.4-1. Subsequent SOX doses may be administered within dosing windows per package insert or local standard. 
Review Drug Diary during each visit for compliance of twice daily administration of Capecitabine or S-1. Collect Drug Diary at the completion of each cycle.

Abbreviations: BICR = blinded independent central review; BP = blood pressure; C = cycle; D = day; ECG = electrocardiogram; ECOG = Eastern Cooperative Oncology Group; [REDACTED]

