Pregnancy Test (WOCBP only)	X	See Note	Serum or urine (minimum sensitivity equivalent units 25 IU/L or equivalent units of HCG) within 24 hours prior to administration of first dose of study treatment and then every 4 weeks (\pm 7 days) regardless of dosing schedule. If collected with a dosing visit, then obtain within 24 hours prior to administration of study drug. Home pregnancy test that meets the minimum sensitivity requirements can be used as necessary.
ECG	See Note	See Note	Cycle 1: Performed within 72 hours prior to dosing on Days 1 and 15 Cycles 2-4: Performed within 72 hours prior to dosing on Day 1. Cycle 5 and Beyond: Performed within 72 hours prior to dosing every 12 weeks starting with C5D1
Efficacy Assessments			
Body imaging	See Note		See Section 9.1.1 . Tumor assessments should occur every 6 weeks (\pm 7 days) starting from randomization up to and including Week 48, then every 12 weeks (\pm 7 days) regardless

Table 2-3: On-treatment Assessments - Participants Assigned to Investigator’s Choice FOLFOX (CA224060)

Procedure ^a	Cycle 1 Day 1 (Cycle = 6 weeks)	Other Time Points Relative to Dosing Schedule	Notes
			of treatment schedule until BICR-confirmed PD or the participant withdraws consent, whichever comes first. Participants who discontinue study treatment for reasons other than PD will continue to have tumor assessments until their disease progresses or they withdraw consent. Use same imaging method as was used at screening/baseline
Brain Imaging		See Note	See Section 9.1.1 . Participants with a history of brain metastasis or symptoms should have surveillance MRI per standard of care (approximately every 12 weeks), or sooner if clinically indicated
Study Treatment			
Randomization	X		Contact IRT for randomization
BMS-986213, or Nivolumab	X	See Note	First dose of BMS-986213 or nivolumab and FOLFOX should be administered within 72 hours after randomization. BMS-986213 or nivolumab should be administered every 4-weeks on the same day as FOLFOX, unless there is a dose delay or treatment is discontinued. BMS-986213 or nivolumab may be administered within 3 days before or after the scheduled date if necessary. BMS-986213 should be administered in a single IV bag over 60 minutes. Nivolumab should be administered over 30 minutes.

Table 2-3: On-treatment Assessments - Participants Assigned to Investigator’s Choice FOLFOX (CA224060)

Procedure ^a	Cycle 1 Day 1 (Cycle = 6 weeks)	Other Time Points Relative to Dosing Schedule	Notes

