FOLFOX	X	See Note	First dose to be administered within 72 hours after randomization. FOLFOX dose schedule: see Table 7.1.3-1 . Subsequent FOLFOX doses may be administered within dosing windows per package insert or local standard.

Abbreviations: BP = blood pressure; C = cycle; D = day; ECG = electrocardiogram; ECOG = Eastern Cooperative Oncology Group; [REDACTED]
[REDACTED] FOLFOX = oxaliplatin, leucovorin, and fluorouracil; FU = Follow-up; HCG = human chorionic gonadotropin; IV = intravenous; NCI CTCAE = National Cancer Institute Common Terminology Criteria for Adverse Events; MRI = magnetic resonance imaging; [REDACTED]
[REDACTED] SAE = serious adverse event; concentration; [REDACTED] WOCBP = women of childbearing potential

^a If a dose is delayed, the procedures scheduled for that same time point should also be delayed to coincide with when that time point’s dosing actually occurs, except for body imaging, [REDACTED] and pregnancy testing.

Table 2-4: Follow-up Assessments - All Participants (CA224060)

Procedure	Follow-Up ^a Visits 1 and 2	Survival Follow-Up Visits ^b	Notes
Safety Assessments			
Targeted Physical Examination	X		Weight, BP, HR, and temperature. Targeted physical examination to be performed only as clinically indicated.
Serious Adverse Events Assessments	X		Assessed using NCI CTCAE v5
Adverse Events Assessment	X		Assessed using NCI CTCAE v5
Review of Subsequent Cancer Therapy	X	X	
Laboratory Tests	See Note		For Follow-up Visit 1, including Hematology, Serum Chemistry, and Urinalysis as outlined in Table 9.4.4-1 . Repeat at Follow-up Visit 2 if study treatment related toxicity persists.
Pregnancy Test (WOCBP only)	See Note		Serum or urine pregnancy testing is only required at FU1 and FU2 visits, unless increased frequency and duration is required per local regulations.

Table 2-4: Follow-up Assessments - All Participants (CA224060)

Procedure	Follow-Up ^a Visits 1 and 2	Survival Follow-Up Visits ^b	Notes
Efficacy Assessments			
Body imaging	See Note	See Note	See Section 9.1.1. For participants who discontinue study drug for reasons other than PD, follow-up scans should be performed every 6 weeks (± 7 days) up to and including Week 48, then every 12 weeks (± 7 days) until BICR confirmed PD, lost to follow-up, or withdrawal of consent. Radiographic assessments should be Q12W in Follow-Up and not be delayed until follow-up visits 1 & 2.

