9.1.4 BICR Confirmation of Progression

Sites should submit all scans to the imaging core lab on a rolling basis, preferably within 7 days of scan acquisition, throughout the duration of the study. BICR of scans will occur on a rolling basis, blinded to treatment arm, clinical data, and investigator assessment of submitted scans. When progression per RECIST 1.1 criteria is assessed by the investigator, the site will inform the imaging core lab, so that the BICR assessment of progression can be performed. The BICR review will be completed and the results provided to the site within 5 days of receipt of the scans, provided there are no pending imaging queries to the site.

Participants whose progression is not confirmed by the BICR will be required to continue tumor assessments (if clinically feasible) according to the protocol-specified schedule, or sooner if clinically indicated. Also, if participants discontinue treatment without radiographic progression, tumor assessments will continue according to the protocol specified schedule, as noted in [Section 2](#), until progression has been confirmed by BICR.

All study treatment decisions will be based on the investigator's assessment of tumor images and not on the BICR assessment. The BICR assessment of progression is only relevant for determining when tumor assessments for a given participant are no longer required to be submitted to the imaging vendor.

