4.1.3 Progression-Free Survival

Two definitions are used for analysis of Progression-Free Survival (PFS). The primary definition accounts for subsequent therapy by censoring at the last evaluable tumor assessment on or prior to the date of subsequent therapy. The secondary definition is irrespective of subsequent therapy and does not account for subsequent therapy.

Clinical deterioration in the absence of unequivocal evidence of progression (per RECIST v1.1 criteria) is not considered progression for purposes of determining PFS.

The first on-study tumor assessment is scheduled to be conducted at 12 weeks (± 1 week) following randomization. Subsequent tumor assessments are scheduled every 6 weeks (± 1 week) up to 13 months, then every 12 weeks until disease progression.

When the objective is specific to the investigator assessment, the above definition is altered to exchange BICR for investigator assessment in the derivation of the endpoint.

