7.5.8 Current Status of PFS and OS Follow-up

The extent of follow-up for survival, defined as the time between randomization date and last known alive date (for subjects who are alive) or death date (for subjects who died), will be summarized descriptively (median, min, max) in months for all randomized populations.

The currentness of follow-up for survival, defined as the time between last OS contact (i.e., last known alive date or death date) and cutoff date (defined by last patient last visit date), will be summarized in months for all randomized subjects. Subjects who died and subjects with last known alive date on or after data cut-off date will have zero value for currentness of follow-up.

Minimum follow-up for OS, defined as the time from cutoff date to last subject's randomization date, will be summarized in months for all randomized subjects.

Time from last evaluable tumor assessment to cutoff date in months will be summarized by treatment group and overall for all randomized subjects. Subjects who have a PFS event will be considered as current for this analysis. The secondary definition of PFS will be used for this summary.

By-subject listing will also be produced to accompany the subject time from last evaluable tumor assessment.

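### Protocol 9.1.1 stops scans at subsequent therapy, but the schedule tables, Protocol 9.1.4 and the SAP's secondary PFS definition need them to continue to BICR-confirmed progression

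*Protocol*

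**What the plan says.** Two rules for ending tumor imaging stand in the current protocol.

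- **Protocol 9.1.1** sends sites to Tables 2-2, 2-3 and 2-4 and, in the same sentence, runs imaging "until participant has confirmed progression by BICR, subsequent therapy is started", or the patient withdraws consent or is lost to follow-up.
- **Table 2-2 (XELOX/SOX)**: "Participants who discontinue study treatment for reasons other than PD will continue to have tumor assessments until their disease progresses or they withdraw consent".
- **Table 2-3 (FOLFOX)**: imaging is regardless "of treatment schedule until BICR-confirmed PD or the participant withdraws consent, whichever comes first".
- **Table 2-4 (follow-up)**, for patients who stop study drug for reasons other than progression: "until BICR confirmed PD, lost to follow-up, or withdrawal of consent".
- **Protocol 9.1.4**: "Participants whose progression is not confirmed by the BICR will be required to continue tumor assessments", qualified by clinical feasibility. Patients who stop treatment without radiographic progression also continue until BICR confirms it.

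Only 9.1.1 lists subsequent therapy as an end point for imaging.

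On the analysis side, SAP 4.1.3 sets out two PFS definitions. The primary one censors at the last evaluable scan on or before subsequent therapy. Of the other it says: "The secondary definition is irrespective of subsequent therapy and does not account for subsequent therapy". Under SAP 4.1.3.2, a death without recorded progression is an event on the death date, and a patient alive without progression is censored at the last evaluable scan. Nothing covers a long gap between last scan and death. SAP 7.5.4 uses the primary definition and makes the secondary analysis optional. SAP 7.5.8, which summarises time from last evaluable scan to cutoff, is not optional: "The secondary definition of PFS will be used for this summary".

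**The concern.** A site cannot obey both rules. The gap concerns patients who start new therapy before BICR confirms progression. One route is explicit in 9.1.4: treatment decisions follow the investigator's reading, so a patient can leave treatment for a progression that BICR does not confirm. Another is stopping study drug for a reason other than progression and then starting something else.

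For such a patient, 9.1.1 ends the scans that an ITT-type PFS needs. The analysis then handles the switch in one of two ways. If the patient dies before cutoff, the death date stands in for an earlier progression nobody looked for. If the patient is alive, follow-up is cut back to the last pre-switch scan, which is what the primary definition already does. The secondary definition then does not deliver what its wording says. Living switchers without BICR progression would also appear in SAP 7.5.8 as patients whose imaging has lapsed, although the site did what 9.1.1 told it to do.

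**Working it through.** **Which analyses need scans after a switch.**

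| Endpoint | Treatment of subsequent therapy | Needs later scans? |
|---|---|---|
| BOR and ORR (SAP 4.1.1) | window closes there | No |
| DOR (SAP 4.1.2) | censored at last scan before it | No |
| PFS, primary (SAP 4.1.3.1) | censored at last scan on or before it | No |
| PFS, secondary (SAP 4.1.3.2) | ignored | Yes |
| Scan currency (SAP 7.5.8) | uses secondary PFS | Yes |

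**Size.** The visible text gives no PFS median, event count, hazard ratio or switching rate, so there is no figure to reproduce. The simulation below shows mechanism and range and is not a forecast for this trial.

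From the documents: scans every 6 weeks to Week 48, then every 12 (Tables 2-2, 2-3); 16 months' accrual and a 22-month primary analysis (Protocol 5.3); later cutoffs at 16 + 9 = 25 months (Protocol 10.3.9) and 16 + 60 = 76 months (Protocol 5.3).

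Assumed: exponential times; median time to progression / median survival after progression of 8/6, 6/4 or 8/9 months; 10% or 30% switching before BICR progression, either within one 6-week scan interval of it (late) or uniformly before it.

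The SAP 4.1.3.2 rules were applied twice, with scans continued and with scans stopped at the switch. At month 22, in months:

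| Switch timing | Medians | Continued | Stopped, 10% / 30% switch | Affected patients with a death event |
|---|---|---|---|---|
| late | 8/6 | 8.28 | 9.66 / 10.28 | 57–58% |
| late | 6/4 | 6.90 | 6.90 / 8.28 | 71% |
| late | 8/9 | 8.28 | 9.66 / 11.04 | 45% |
| uniform | 8/6 | 8.28 | 9.22 / 9.66 | 46% |
| uniform | 6/4 | 6.90 | 6.90 / 7.46 | 61% |
| uniform | 8/9 | 8.28 | 9.59 / 9.66 | 36–37% |

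- Shift in the median: from 6.90 − 6.90 = 0 to 11.04 − 8.28 = 2.76 months. Medians sit on the scan grid (36 weeks × 7 / 30.4375 = 8.28 months), so they move in steps.
- The remaining 29–64% of affected patients are alive and censored at the last pre-switch scan.
- Where a death replaces a progression that would have been seen, the date moves by a median of 2.1–3.3 months at month 22, 2.4–3.9 at month 25 and 3.2–8.3 at month 76.

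**Hazard ratio** (8/6 medians in the control arm; true HR 1.0 or 0.75; cutoffs 22 and 76 months). Factor = HR with scans stopped ÷ HR with scans continued, in the same simulated patients:

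| Switching, control / experimental | Smallest change | Largest change |
|---|---|---|
| 20% / 20% | 1.010/1.009 = 1.001 | 0.750/0.735 = 1.020 |
| 30% / 10% | 1.076/1.012 = 1.063 | 1.143/1.008 = 1.134 |
| 10% / 30% | 0.925/0.979 = 0.945 | 0.862/0.971 = 0.888 |

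The arm that switches more looks better. For scale, a 70% CI for the log HR has half-width of about 1.036 × 2/√D. With an assumed D of 100 to 200 events that is 0.21 to 0.15, against ln 1.06 = 0.06 to ln 1.13 = 0.12.

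**The case against.** The strongest reply is that little rests on this. The planned PFS comparison uses the primary definition, SAP 7.5.4 only permits the secondary one, and SAP 7.5 calls everything beyond the primary endpoint descriptive. That stands, and it limits the point to one optional analysis and one descriptive summary.

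A second reply is that 9.1.1 also asks for any additional imaging, including scans from outside institutions, to go to BICR, with no exception after a switch. This stands in part. It collects scans that happen to be done but requires none and sets no timing, so ascertainment would vary by site.

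A reader might infer several stronger things that the documents do not support:

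- **That early switching will be common.** No rate is given. BICR results are due within 5 days of scan receipt absent queries (9.1.4), and treatment beyond progression is allowed (7.3.8). Both could limit it.
- **That unobserved progressions simply become much later deaths.** Switchers alive at cutoff are censored, and at month 22 the simulated delay for those who die is about 2 to 3 months.
- **That the secondary PFS is the planned check on informative censoring.** The SAP defines it but does not state that purpose.
- **That the treatment comparison is biased regardless.** That needs unequal switching between arms.

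**Conclusion.** The contradiction between Protocol 9.1.1 and both the schedule tables and 9.1.4 is real and in current text. If 9.1.1 is followed, the secondary PFS for patients who switch before BICR progression mixes death-dated events with censoring at the last pre-switch scan, so it is not an ITT analysis in the sense the SAP intends. Switchers alive without BICR progression would also be misread as lapsed in SAP 7.5.8.

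The primary ORR result, DOR and the main PFS analysis are untouched. The size cannot be read from the documents: every figure above depends on assumed progression, survival and switching inputs, and the hazard-ratio distortion also depends on the assumed imbalance between arms. The inconsistency is worth correcting because missed scans cannot be recovered; it does not threaten the trial's main conclusion.

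**What to change.** Delete the subsequent-therapy clause from Protocol 9.1.1 so that it agrees with Tables 2-2 to 2-4 and 9.1.4. This adds no scans beyond those the schedule already requires. The cost is a protocol revision or administrative letter with the usual ethics committee handling (Appendix 2). The SAP already describes enrolment in the past tense when it drops region as a stratification factor, so the edit cannot restore scans already missed.

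If the stop is kept, or for scans already missed, two SAP changes suffice and need no new data:

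1. Do not present the secondary PFS as an ITT analysis without reporting, by arm, how many deaths were counted as events after a switch with no intervening scan.
2. In SAP 7.5.8, show patients whose scans stopped at subsequent therapy as a separate category.

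Moving SAP 7.5.8 to the primary definition would not help. Switchers are censored there without an event, so they would still appear non-current, including those who later progress or die.
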